***iCaminemos Juntas!* only measures:**

Accelerometry and App Usage: Better understanding of the feasibility, accuracy, and added value of accelerometry will inform commercialization efforts. Fitbit® devices will monitor PA for participants who own that device. The Fitbit® will automatically record daily step data in the *iCaminemos Juntas!* app and progress towards the steps/day goal will be graphically presented on the app, using a color-coded graph automatically sent to the participant's phone. For participants who do not own a Fitbit®, the phone's built-in GPS will record the route walked. Data on the time spent during the walk plus the distance derived from the GPS and the walking pace provided by the user in her profile will be combined to estimate steps. *iCaminemos Juntas!* participants will also enter other exercise activities (non-*Caminemos* walks) (minutes/day) using the app. User-entered data will be compared to PA data gathered using the Fitbit® or LBS distance tracking feature.

App usage will be measured by having participants register on the server when downloading the *iCaminemos Juntas!* app. The server will record the number of times (date and time) the app connects to the server and users use various app features (number of uses, initiating walks, accepting walks, app tools used, etc.). Ecological momentary assessment (EMA) will be utilized to evaluate the app's ease of use. EMA's repeated sampling of experiences and behaviors in real time at random intervals should minimize recall bias and increase ecological validity,¹⁸⁸⁻¹⁹⁰ highlight individual differences in behavior and distribution over time, and detect factors affecting behavior.¹⁹¹⁻¹⁹⁵ EMA will be used to assess level of interest and likability of the *iCaminemos Juntas!* app. Participants randomized to that condition will be sent "push notifications" via the app once a week at various times of day that ask them to rate their opinions on the app. Users will also evaluate the app on the System Usability Scale at the 12-week post-test.¹³⁴

3C.6.3. *iCaminemos Juntas!* Intervention (n=100). A description of the *iCaminemos Juntas!* app was provided in **Section 3C.4.** Participants will download the app following the procedures outlined in **Section 3C.7.1.** Project staff will provide *iCaminemos Juntas!* users a one-one-orientation to the app and how to use its unique features. Daily alerts and notifications will engage users in daily use of the app and provide up-to-date information on users' progress. Participant responses will also be used to evaluate additional or on-going support of users' needs (e.g., increase/ decrease prompts based on user preferences, tailored messages around a set goal, etc.). To protect privacy and to ensure that the participant is the person completing the app activities, KB will uniquely identify the user's smartphone based off the device's "hardware footprint". The app will upload all app activity data to the KB secured web server database.

3C.6.4. World Walking App Comparison Group (n=100). *World Walking* (www.worldwalking.org) is an app available for free on both iOS and Android platforms.¹⁹⁶ It allows users to track walking steps using the phone's LBS features, display walks on a virtual route, create virtual walking groups (you and other users can have shared goals for walking a certain distance such as walking the Great Wall of China), chat with virtual group members, earn badges for meeting goals, connect to Fitbit, and receive push notifications. There are a number of similarities between the two apps; participants will be able to track their walking, have a reward-based system for meeting goals, map their walks, use Fitbit, and have a social network component. The app encourages social interaction by letting walkers form virtual clubs, working together to meet distance targets.

However, while there are similarities between the two apps, *World Walking* will not allow for real-time, in-person social connection (meeting other women in-person and walking locally), or connection to social media.

Selecting the best comparison condition is a critical question when designing a RCT.¹⁹⁷ We considered a number of possible control conditions (e.g., no treatment control, waitlist control, etc.). Initially, we considered a 3-arm design (*Caminemos* vs. *World Walking* vs. No treatment) but rejected it due to resource demands, need for more programming, and large sample size to obtain sufficient power. The purpose of a Phase II grant is to continue the research and development efforts initiated in Phase I and prepare for commercialization objectives resulting from the Phase I and II activities. Our primary goal is to determine if the *iCaminemos Juntas!* app is more effective at improving PA behavior compared to other products available in the market. Therefore, we decided to choose an active control app that was: (a) readily available; (b) had features similar to the *iCaminemos Juntas!* app; and (c) had scientific merit. Our study design choice was a comparative effectiveness trial so choosing an existing app with similar features (i.e., a potential market competitor) was paramount. It was this high level of similarities that made *World Walking* a reasonable comparator.

3C.6.5. Adherence, Dropouts, and Participant Compensation.

Retention, Tracking, and Attrition: Although participants can withdraw at any time, steps will be used to minimize dropouts to ensure high internal validity. Participant progression will be tracked. Staff will use behavioral reinforcement strategies known to be effective in the behavior change literature¹⁹⁸⁻²⁰⁰ and be trained to develop rapport with participants by communicating expectations for participants and staff. Personalizing this relationship will enable participants to be more direct about problems, providing a strong foundation for problem-solving. While drop-out rates vary in community walking program for Latinos, we conservatively planned for 20% attrition.²⁰¹ Our Phase I attrition was 10%. We assume equal adherence across the two treatment groups, because we have no data to predict otherwise. Our method of tracking and multiple contacts will help us retain some of these participants for intent-to-treat purposes, despite their discontinued app use. Participants will provide contact information for two individuals who can always contact them and update contact information at each assessment. If they do not respond to email/text reminders, we will follow-up by phone. Finally, we will create a dummy coded variable for each respondent where 1=completers and 2= drop outs and test for associations with key variables in our analytic models. If bias is identified, we will control for it by adding it as a covariate.

Compensation: All participants (n=200) will be compensated to incentivize and improve study retention. A \$100 gift card will be given for completing all study assessments (baseline, 6-week, and 12-week).

App Use: Implementation of technology-based interventions can be challenging due to participants forgetting, fatiguing, or believing they have learned all they need to know. In order to bolster compliance with using either of the assigned app, weekly reminders to use the app will be sent to participants by text message.

3C.6.6. Safety Considerations. Participant safety is a priority. This study will include a Data and Safety Monitoring Plan (DSMP) plus IRB approvals. The team will monitor progress, discuss concerns, problem-solve, and take corrective actions. [name] (PI) is a licensed psychologist in Colorado (#3630) and Louisiana (#1197) and will assemble a group of experts including at least one licensed mental health professional and one biostatistician. Participants who express distress will be referred to local community centers which provide health and mental wellness outreach. Based on our experience and demonstrated ability to conduct this type of research, we are confident we can achieve safe intervention delivery.

3C.7. Data Collection, Management, and Security. KB has used online data collection successfully in a number of studies. Study consents and pretests and posttests will be collected online via a tablet computer. Six-week assessments will be collected online over participants' personal smartphones or computer devices. Surveys will be programmed using QuestionPro software on KB's secure web server to ensure a structured approach and reduce errors/missing values. All procedures will be approved by KB and Stanford IRBs.

KB has considerable experience maintaining large databases and ensuring high-quality data. [name], KB's Biostatistical Manager, will supervise data management. All data will be uploaded in real-time using KB's secured network; data will be de-identified and stored in KB's secured database. Established KB protocols for quality assurance (valid ranges; internal consistency checks, etc.) will ensure high quality data. The KB data team will compile master data files. Survey and app usage data will be linked. Missing data should be limited since data is recorded electronically. Staff will identify missing responses and check that entries were not intentionally skipped. Analyses will be done on data collected. While unlikely, data may not be missing at random (NMAR). KB will assign all lost responses to extreme category and perform multiple imputation procedures that can handle various amounts of missing data and use covariates and propensity scores.

Data security: KB's server farm has 5 Dell PowerEdge servers with two 3.2 Ghz Xeon processors, four with 32 gigabytes of RAM and one with 64 gigabytes, and three 1 Terabyte hard drives that operate off a hardware RAID5 system, connected to a local area network (LAN) running the Windows 2008 or 2012 operating system and to the Internet through a 20-megabyte Fiber connection. KB programmers monitor and maintain all programs and databases. Sensitive information is protected by a hardware firewall (Cisco ASA 5505) and each server has its own native Windows security software. All KB servers are connected via 1 Gigabit high-speed switched network, ensuring high-speed transfer between machines. All networked computers are protected from viruses by Sunbelt Vipre Enterprise. Nightly backup of each computer protects against the loss of data.

3C.8. Statistical Power Calculations and Analysis.

Sample size: We expect results similar to those previously revealed in a study by Co-I, [name].²⁰² In that study, participants in a peer mentor arm reported an average increase of moderate-to-vigorous physical activity of 216.2 minutes/week ($SD = 355.7$) from baseline to 12 months compared to a 178.0 minutes/week ($SD = 234.9$) increase among those in the comparison arm. The comparison arm increased an average of 71.5 minutes/week ($SD = 179.1$) from baseline to 12 months. Comparing the two arms, with a change of 71.5 minutes/week, shows sample sizes of 81 and 81 achieve 90% power to reject the null hypothesis of equal means when the population mean difference is 144.7 with standard deviations of 355.7 for peer mentor arm and 179.1 for the comparison arm, and with a significance level (alpha) of 0.05 using a two-sided two-sample unequal-variance t-test. Adjusting for a conservative level of dropout at 20% allows for 100 per group for a total sample size of 200. If our active arm is similar to the comparison arm, because of the smaller standard deviation, the sample size necessary to achieve 90% power only increases to 82 per group, despite the lowered difference.

Analyses:

There 3 specific aims that will be evaluated. The analyses for Aims 1 and 2 are heavily descriptive in nature. Means (standard deviations), medians (Interquartile range), distributions, frequencies and percentiles, etc. will be used to characterize the outcome measures.

Aim 1 will be assessed by examining the number of connections/matches for walking (creating and/or joining a walk). We believe that at least 70% of the *iCaminemos Juntas!* intervention group will establish at least one connection and participate in at least one walk (e.g., 78% of users in Phase I created at least one walk). The distribution of number of connections and walks completed will be examined. We will test whether there is a difference between the groups in connections that occurred using a chi square test and will further test a single proportion that the *iCaminemos Juntas!* group will have significantly more than 70% active participation as evidenced by making at least 1 connection.

Aim 2 will be evaluated descriptively and via feasibility testing showing that location-based services can be replicated regardless of region.

Aim 3 is critical to product development and will evaluate whether *iCaminemos Juntas!* increases physical activity, social support, and quality of life (QOL) in Latinas. Three hypotheses for the comparative-effectiveness trial will be examined:

H₁: Latinas randomized to the *iCaminemos Juntas!* app will report greater improvements in their physical activity compared to Latinas randomized to the comparison app (*World Walking* app) at 12-weeks post-test.

H₂: Latinas randomized to the *iCaminemos Juntas!* app will report greater increases in their social support for exercise compared to Latinas randomized to the comparison app at 12-weeks post-test.

H₃: Latinas randomized to the *iCaminemos Juntas!* app will report greater improvements in their quality of life (QOL) compared to Latinas randomized to the comparison app at 12-weeks post-test.

Additional secondary analyses will (1) evaluate immediate changes in the PA, social and environmental support, and QOL measures at 6 weeks; (2) assess mediators at 6-weeks for a mediational analysis on 12-week outcomes; and (3) evaluate app usage data (e.g., number of log-ins, number of “check-ins”, EMA responses for likability and satisfaction with the app).

Tests will be performed as per the design using simple t-tests followed by analysis of covariance to assess the outcome results adjusted for baseline (rather than change from baseline). Multivariate analyses will be conducted to assess the simultaneous direction of changes in the components between the treatment arms. We will test the outcomes simultaneously and examine the correlation amongst them within treatment arms. Hotelling’s T² will be used to test the overall mean vector of responses. This analysis will utilize the pre- and post-measures, but additional analyses will be conducted using generalized least squares regression (PROC MIXED in SAS ver 9.3 or higher) to account for missing data (drop outs between 6 weeks and 12 weeks).

Characteristics of dropouts and/or noncompliant individuals (those who do not walk and/or form any connections) will be intensively examined to shed light on potential weaknesses of the app (differential dropout overall or within certain subgroups). The evaluation of the app will include its impact using the pre-post data. As noted, examination of the correlation matrices along with the mean changes will inform whether the variables appear to move similarly in both groups. Thus, one might argue that it is not necessarily the best control choice since we would then be measuring the intensity of intervention. Alternatively, very different correlation structures will inform us about how the interventions are working and may provide information on appropriate controls and or strengths and weaknesses.

Utilization data will be examined to understand the acceptability and intensity of interactions with the apps. The penetration of the apps into this minority at-risk population is very important in potentially understanding, not only market share, but also potential impact. Complier average causal effect models²⁰³ will be used to examine the intensity of the intervention app’s utilization. Mediation models using the latest bootstrapping methods^{204,205} will be examined to enhance evidence that the changes induced by the treatment effects are consistent with the changes being mediated via the app and the intervention.

3C.9. Design Strengths, Potential Limitations, and Overall Impact. The study has numerous strengths and few limitations. We will use the latest technology for iPhone and Android systems. The app will be thoroughly tested, and user-friendly and effectiveness will be evaluated in a randomized design. The study team and environment are strong. KB is a leader in the development of health behavior research technology, and Stanford has a strong history with the conduct of clinical trials. Drs. [name] and [name] have extensive clinical trials experience and expertise in the behavioral PA content to be delivered and have competent research teams and resources to assist them. Potential study limitations are: (1) difficulty recruiting; (2) sample homogeneity; and (3) sources of bias (measurement; demand effects). We have tried to reduce these. We will work closely with the CAB to maximize our potential to recruit Latinas. While the study will only be conducted with Latinas residing in Denver and San Jose; studies suggest that poor PA habits are common among Latinas implying that the sample will represent the target population rather than just the Denver and San Jose populations. Outcomes are self-reported and open to bias; however, the use of validated measures is a strength.

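### The lead H1 tests drop women lost by week 12 and ignore their 6-week activity scores; the planned mixed model that would use them is only additional, and no rule says which result decides H1

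*Combined protocol and SAP*

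**What the plan says.** H1 (section 3C.8, Analyses) compares improvement in physical activity between the arms at 12 weeks. Activity is measured at baseline, week 6 and week 12 (Table 4), and data collected before a withdrawal are kept (section 5B1).

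The handling of missing 12-week scores is spread over three sections:

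- **Section 3C.8, Analyses:** "Tests will be performed as per the design using simple t-tests followed by analysis of covariance", adjusted for baseline. Later in the same paragraph: "This analysis will utilize the pre- and post-measures, but additional analyses will be conducted using generalized least squares regression" in PROC MIXED. The stated purpose of that model is to deal with women who leave between weeks 6 and 12.
- **Section 3C.7:** "Analyses will be done on data collected". Then, after the remark "While unlikely, data may not be missing at random (NMAR"), the plan says: "KB will assign all lost responses to extreme category and perform multiple imputation procedures that can handle various amounts of missing data". The imputation is to use covariates and propensity scores, which are not listed.
- **Section 3C.6.5:** each woman is coded as completer or dropout. The code is tested against key variables and added as a covariate if bias is found.

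On sample size, section 3C.8 says "Adjusting for a conservative level of dropout at 20% allows for 100 per group for a total sample size of 200". The same section expects the study of dropouts to "shed light on potential weaknesses of the app (differential dropout overall or within certain subgroups").

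**The concern.** Several rules are listed, and none is labelled as primary or as sensitivity analysis for H1. A default can be read, because the trial is sized on an unequal-variance t-test of the women who remain after 20% loss. That default uses baseline and week 12 only. The sentence about pre- and post-measures follows the mention of Hotelling's T² and may refer to that test alone, but the point does not depend on it: neither a two-sample t-test on 12-week change nor an ANCOVA adjusted for baseline has a place for week 6.

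At 20% loss about 40 of 200 women would have no primary outcome. If women whose activity has not risen by week 6 are more likely to leave, the completers are a selected group, and the selection need not be equal in the two arms. The 6-week score is the information that could correct for this. The plan collects it and has a model for it, but does not give that model the H1 decision. Several differing H1 results could then be reported with no rule for choosing among them.

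**Working it through.** **1. The plan's sample size.** The inputs are from section 3C.8. The difference is 216.2 - 71.5 = 144.7, with SDs 355.7 and 179.1. The standard error at 81 per arm is √[(355.7² + 179.1²)/81] = 44.25, and Welch power is 0.900. In the second scenario ("If our active arm is similar to the comparison arm, because of the smaller standard deviation") the difference is 178.0 - 71.5 = 106.5, with SDs 234.9 and 179.1. The standard error at 82 per arm is 32.62 and power is 0.900. Both stated sizes reproduce. With 100 × 0.80 = 80 completers per arm, power is 0.897 and 0.893. The sizing is not at fault.

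**2. What each listed rule does with a woman seen at week 6 and lost by week 12.**

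| Rule | Effect |
|---|---|
| t-test, ANCOVA on observed data | She is excluded and her week-6 score is unused |
| Completer/dropout covariate in that ANCOVA | It is constant among completers. A design with intercept, arm, baseline and the code still has rank 3, so nothing changes |
| The same covariate in a mixed model or after a fill | It is a post-randomisation variable, entered after seeing the data |
| Extreme-category fill | No value, direction or scope is given for minutes per week |
| Multiple imputation | It could recover the loss if week 6 is in the model; not stated |
| PROC MIXED | It uses her week-6 score; listed as additional |

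**3. Bias under one dropout rule for both arms.** Let X and Y be the 6- and 12-week changes, with the same SD within an arm and correlation ρ. If dropout depends on X only, then

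bias = ρ × {[E(X | completer) - E(X)] in the app arm - the same shift in the comparison arm}.

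The assumptions, none of them in the documents, are: the logit of dropout falls by 0.6 or 1.2 per 250 min/week of X; one intercept gives 20% loss overall; ρ is 0.4 or 0.6; mean change at week 6 is half or all of that at week 12. The shifts come from numerical integration. The two ends of the range in each SD setting are:

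| SDs (app/comparison), true effect | Smallest | Largest |
|---|---|---|
| 355.7/179.1, 144.7 | 0.4 × (50.61 - 16.06) = +13.8 | 0.6 × (89.02 - 26.71) = +37.4 |
| 234.9/179.1, 106.5 | 0.4 × (23.16 - 16.18) = +2.8 | 0.6 × (42.54 - 28.77) = +8.3 |
| 179.1/179.1, 106.5 | 0.4 × (14.23 - 15.68) = -0.6 | 0.6 × (22.85 - 32.30) = -5.7 |

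At 10% loss the ranges are +7 to +23, +1 to +5 and -3.5 to -0.3.

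Adjusting for baseline does not remove the bias. With an assumed baseline-to-change correlation of 0 or -0.4, the ANCOVA bias at 20% loss is +12 to +38, +3 to +8 and -6 to 0. A likelihood estimate that uses week 6 returns 144.4-145.0, 106.3-106.7 and 106.3-106.8.

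**4. Type I error.** With no true effect and the same dropout rule (20,000 simulated trials per setting, 100 per arm), the Welch test rejects in 0.07-0.17, 0.05-0.07 and 0.05 of trials in the three SD settings. The week-6 analysis rejects in 0.046-0.051.

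**5. Dropout patterns that differ by arm.** A separate simulation used 100 per arm, a common SD of √[(355.7² + 179.1²)/2] = 281.6, correlations of 0.3, 0.5 or 0.7 between visits, about 20% loss per arm, and a true effect of 144.7. Observed-data ANCOVA gave 145-146 when low week-6 scorers left both arms alike, 157-161 when dropout followed week 6 in one arm only, and 170-179 when the patterns were opposite. With no true effect it rejected in about 5%, 6-8% and 10-16% of runs. With the true effect at 144.7, the estimate using week 6 was 141.5-146.4 throughout.

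**The case against.** The strongest reply is that the remedy is already in the plan. PROC MIXED is scheduled for just these women, so a reader who infers that the plan has no method for them would be wrong. That stands: the fault is one of rank, not of absence.

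Multiple imputation could also repair the loss. The plan neither includes nor excludes week 6 from its covariates, so the fair description is unspecified, not inadequate.

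A reader might also infer that an extreme value would be put in place of every missing 12-week score, diluting the effect and costing power. The text does not support that. The words refer to responses and categories, the sentence follows a check on skipped entries, and it comes after a remark that calls the situation unlikely. It may cover skipped items only. No fill value is given, so no effect of a fill is quantified here.

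The size of the bias is also open to challenge. It is small except at SDs of 355.7/179.1, and those are 12-month changes from another study, not 12-week app data. With equal SDs and one dropout rule, type I error stays at 0.05. Phase I attrition was 10%, the plan calls 20% conservative, and staff will try to keep women in follow-up after they stop using the app. These points lower the likely bias but do not remove the question of which result decides H1.

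**Conclusion.** The concern holds, at moderate weight. The documents do not assign H1 to one analysis, and the analysis most naturally read as the lead one leaves out 6-week data that the trial will hold. Under equal random loss that default is unbiased, with power of about 0.89 to 0.90.

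If dropout follows early response, the bias may be anywhere from a few minutes per week in either direction to about a quarter of the planned effect (37.4/144.7 = 26%). Its sign depends on the SDs, so it would be wrong to infer that the plan must favour the app. It can be larger where dropout patterns differ by arm, a possibility the plan itself raises. All these figures are conditional on assumed dropout slopes and correlations. What does not depend on them is that the completer/dropout covariate cannot correct an observed-data ANCOVA.

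**What to change.** Name the planned PROC MIXED model as the primary H1 analysis: all randomised women; baseline, 6-week and 12-week activity; arm-by-time terms; variances allowed to differ by arm, because the planning SDs differ about 2:1; and the 12-week arm contrast as the test. Keep the t-test and ANCOVA as supportive. Use the completer/dropout indicator for description only. Do not apply the extreme-category fill to missing 12-week assessments: restrict it to skipped items with a written scoring rule, or drop it. Specify multiple imputation that includes week 6, with a delta shift, as the not-at-random sensitivity analysis. Settle this before outcome data are seen.

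The cost is plan wording and modest programming. Under equal random loss, a likelihood contrast using week 6 had power 0.90-0.92 against 0.89-0.90 for Welch in the two planning scenarios. It was not compared with the planned ANCOVA.

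The downside is that the model assumes missing at random and helps only where week 6 was observed. If half the dropouts also lack week 6, about +6 to +17 min/week of bias remains at SDs 355.7/179.1 and +1 to +4 at 234.9/179.1. If dropout depends on the 12-week value itself, 22-44 of 34-51 min/week remains in the first setting and 5-7 of 7-8 in the second. This is why the delta analysis is needed.

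### Does giving the comparison arm two different gains (178.0 and 71.5 min/week) undermine the sample size of 200?

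*Combined protocol and SAP*

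**What the plan says.** The sample-size paragraph of section 3C.8 opens by tying expectations to an earlier trial: "We expect results similar to those previously revealed in a study by Co-I". It reports a gain of 216.2 min/week (SD 355.7) in a peer mentor arm. It then gives the comparison arm two gains in successive sentences: "compared to a 178.0 minutes/week ($SD = 234.9$) increase among those in the comparison arm. The comparison arm increased an average of 71.5 minutes/week" (the second with SD 179.1).

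The calculation puts 81 participants in each group for a power of 90%, and states the condition on the effect: "reject the null hypothesis of equal means when the population mean difference is 144.7". The spread is taken as 355.7 among the peer-mentored and 179.1 in the other group, and the test is a Welch t-test at two-sided 0.05. Allowing for 20% dropout, it enrols 100 per group. A second scenario begins "If our active arm is similar to the comparison arm, because of the smaller standard deviation" and reports that the requirement rises only to 82 per group.

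On the comparator, section 3C.6.4 explains: "we decided to choose an active control app that was: (a) readily available". It adds that similarity of features made World Walking a reasonable choice. The same section notes that World Walking does not arrange in-person meetings between users.

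**The concern.** Two means and two SDs under one name, over the same 12 months, is a contradiction in the only paragraph that supports n=200. If the comparison arm really gained 178.0, the planned trial would be badly underpowered. The label returns in the second scenario, where reading it as the 71.5 arm makes no sense, because the difference would then be zero.

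There is also a question of substance. Once the arms are sorted out, both 90% scenarios vary only the study app's gain and keep the comparator at 71.5. World Walking is an active app chosen for its likeness to the study app, and the stated goal is to beat products already on the market. A reader may fairly ask why it should behave like the arm with the smallest gain, and how much power is lost if it does better.

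**Working it through.** **Inputs, all from section 3C.8.** Gains (SD) in min/week: 216.2 (355.7), 178.0 (234.9), 71.5 (179.1). Two-sided alpha 0.05, Welch t-test, target power 90%, 20% dropout from 100 per group.

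**Method.** With n per arm, SE = √[(s₁² + s₂²)/n] and the noncentrality is difference/SE. Power comes from the noncentral t with Satterthwaite degrees of freedom.

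**Reproducing 81.** The difference is 216.2 − 71.5 = 144.7. The variance sum is 355.7² + 179.1² = 126,522.5 + 32,076.8 = 158,599.3. At n = 81, SE = √(158,599.3/81) = 44.25, the noncentrality is 144.7/44.25 = 3.27 and power is 90.03%. This matches the plan.

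**Reproducing 82.** The difference is 178.0 − 71.5 = 106.5. The variance sum is 234.9² + 179.1² = 55,178.0 + 32,076.8 = 87,254.8. At n = 82, SE = √(87,254.8/82) = 32.62, the noncentrality is 106.5/32.62 = 3.26 and power is 90.04%. This also matches.

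**Could another reading give the same numbers?** Smallest n per group for 90% power, for each difference and SD pair:

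| Difference | 355.7 / 234.9 | 355.7 / 179.1 | 234.9 / 179.1 |
|---|---|---|---|
| 144.7 | 93 | **81** | 45 |
| 106.5 | 170 | 149 | **82** |
| 38.2 | 1,310 | 1,144 | 630 |

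Only one cell gives 81 and only one gives 82, and both use 71.5 (SD 179.1) as the comparator. The plan's remarks about a smaller SD and a reduced difference in the second scenario also fit: 234.9 is below 355.7, and 106.5 is below 144.7. So 178.0 is the gain of a second active arm, and that arm is what the last sentence means.

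**Power at the enrolled size.** 100 × 0.8 = 80 completers per arm. Power is 89.7% (study app at 216.2) and 89.3% (study app at 178.0). Falling one or two short of 81 or 82 costs less than one percentage point.

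**Dependence on 71.5.** At 80 per arm with the plan's SDs, the difference detectable with 80% power is 125.8 (app at 216.2) or 93.1 (app at 178.0). Unadjusted power therefore falls below 80% when the comparator gains more than 216.2 − 125.8 = 90.4 or 178.0 − 93.1 = 84.9. The margins over 71.5 are 18.9 and 13.4 min/week. At the Phase I attrition of 10% (section 3C.6.5), which leaves 90 per arm, the limits become 97.7 and 90.3.

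**Baseline adjustment.** Section 3C.8 plans an analysis of covariance after the t-tests. Its benefit depends on pre-post correlations that the documents do not give. I assumed a common baseline SD, a common correlation of 0.3 to 0.7, equal pre and post variance in the comparator, and an app-arm follow-up SD set to match the plan's change SD. At 80 per arm the 80% limits are then 90.7–94.6 (app at 216.2) and 86.2–94.8 (app at 178.0), so adjustment adds at most about 10 min/week.

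**The case for a change.** The strongest case for a change is that the comparator's gain is a key uncertain input, and it is the one the plan never varies. The second scenario changes the study app's gain only. World Walking offers tracking, rewards, mapping and virtual groups, and a gain 13 to 19 min/week above the planning value takes unadjusted power below 80%. A sentence saying why the 71.5 arm is the right model, with power at one or two higher comparator gains, would cost almost nothing.

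The dependence is real and the arithmetic stands. It is not hidden, however. For the scenario that sets n, the paragraph names the 71.5 change, the 144.7 difference and the 179.1 SD as the conditions for 90% power, so no back-calculation is needed. Only the closing sentence has to be inferred. Every sample size depends on its assumed effect, and this plan already shows a smaller effect alongside the main one. Any higher comparator gain would be the reader's choice, since the documents give no evidence for a particular value. They do give some reason to expect a lower gain: World Walking lacks the in-person contact that the study app is built on, and section 3A.2 treats social support as a strong driver of activity. A justifying sentence would help the reader, but it would alter nothing in the design.

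**Conclusion.** The label conflict is real and clerical. The 81 and 82 per group are correct on the plan's own inputs, both with 71.5 (SD 179.1) as comparator. The enrolled 200 gives 89.7% and 89.3% power at 80 completers per arm, which is the stated 90% for practical purposes. Renaming the 178.0 arm would change no sample size, test, power or conclusion, and a statistician can settle the reading from the paragraph itself.

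The sensitivity to World Walking's gain is the ordinary conditionality of a power calculation. It would become a fault only if 71.5 were shown to be implausible, and the documents do not show that. The limits of about 90 and 85 min/week rest on 80 completers per arm, the plan's SDs and an unadjusted Welch test. No change to the plan follows.
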